### 6.2 Secondary Endpoint

- Complications and readmissions will be monitored and recorded from the day of the index surgery throughout the extended follow-up.

## 7. Sample Size

The outpatient cohort includes 100 consecutive cases over 5 years. No *priori* power analysis was calculated. The sample size reflects all eligible cases in the study window. In addition to descriptive statistics, the primary inferential analyses will be McNemar and Wilcoxon signed rank tests. A sample size

of 100 is sufficient to reach high power ( $>.99$ ) with a moderate effect size in Wilcoxon signed rank (Cohen's  $d = .5$ ) with alpha level set at .05. For the McNemar tests, we anticipate observing 30-60% patients reporting positive signs/symptoms prior to the surgery and an improvement rate of 70% (the percentage changes from positive at baseline to negative at follow-up). With sample size of 100, the discordant pairs will be 21-42. If no new-onset positive symptom is reported in the follow-up, the McNemar test has power  $> .99$ . If under a more conservative effect where discordant odds ratio is 3 (10-35% patients report new positive symptoms, depending on the baseline prevalence), it will still yield to power .72-.9. Therefore, sample size of 100 is sufficient in this study.

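### The upper McNemar power figure of .9 at a discordant odds ratio of 3 does not follow from the protocol's inputs, which give about .97; the 10-35% new-onset figure lacks its denominator

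*Protocol*

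**What the plan says.** All the inputs stand in Protocol section 7 (Sample Size).

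- Cohort: "The outpatient cohort includes 100 consecutive cases over 5 years".
- Baseline: "we anticipate observing 30-60% patients reporting positive signs/symptoms prior to the surgery".
- Change: "an improvement rate of 70% (the percentage changes from positive at baseline to negative at follow-up").
- Discordant pairs: "With sample size of 100, the discordant pairs will be 21-42".
- First scenario: "If no new-onset positive symptom is reported in the follow-up", power is given as above .99.
- Conservative scenario: "discordant odds ratio is 3 (10-35% patients report new positive symptoms, depending on the baseline prevalence), it will still yield to power .72-.9".
- Conclusion: "Therefore, sample size of 100 is sufficient in this study".

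Alpha of .05 is given in the preceding sentence on the Wilcoxon test. The section names neither the McNemar variant nor the sidedness. It also says that no power analysis was done in advance and that "The sample size reflects all eligible cases in the study window".

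**The concern.** The conservative scenario is fully specified, so its power range can be recomputed. The lower figure comes back and the upper one does not. The two ends appear to rest on different counts of discordant pairs.

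The new-onset percentage has a related weakness. It follows a baseline percentage that refers to all patients, so a reader will tend to take it on the same base. Read that way, it contradicts the odds ratio of 3 in the same sentence.

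These figures are the section's only numerical support for the McNemar tests, which carry the neurologic part of the primary endpoint (sections 6.1 and 8). Section 11 says the protocol will be supplied as a supplementary appendix, so readers will be able to check the sum.

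**Working it through.** **Inputs** (section 7): N = 100; baseline prevalence π = .30 to .60; improvement .70; discordant odds ratio 3; alpha .05. Assumptions: this alpha also applies to McNemar, and the test is two-sided.

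**Step 1. Discordant counts.** Improvers = 100 × π × .70. New onset = improvers / 3.

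| π | Improvers | New onset | Total pairs | New onset / baseline-negative | New onset / all |
|---|---|---|---|---|---|
| .30 | 21 | 7 | 28 | 7/70 = 10% | 7% |
| .60 | 42 | 14 | 56 | 14/40 = 35% | 14% |

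The 10% and 35% are the protocol's own figures. They arise only with 7 and 14 new-onset cases, so the protocol's text commits it to 28 and 56 discordant pairs. The 21-42 counts improvers alone.

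**Step 2. No-new-onset scenario.** With 21-42 pairs all in one direction, power exceeds .99, as stated.

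**Step 3. Conservative scenario by a formula that can be checked by hand.** With p10 and p01 the proportions improving and newly positive, s = p10 + p01 and d = p10 − p01, the normal approximation is

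power = Φ[(d√N − 1.96√s) / √(s − d²)].

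- π = .30: s = .28, d = .14. (1.40 − 1.037) / .510 = .711, so power is .761.
- π = .60: s = .56, d = .28. (2.80 − 1.467) / .694 = 1.921, so power is .973.

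**Step 4. Two-sided exact test**, averaged over the discordant count, which is binomial with N = 100 and probability s. Each discordant pair is an improvement with probability .75.

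| π | Total pairs | Power |
|---|---|---|
| .30 | 28 | .712 |
| .35 | 32.7 | .789 |
| .40 | 37.3 | .850 |
| .45 | 42 | .896 |
| .50 | 46.7 | .928 |
| .60 | 56 | .966 |

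The stated .72 matches the first row. The stated .9 matches 42 total pairs (31.5 improve, 10.5 new onset), not 56.

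**Step 5. Can another variant or reading give both .72 and .9?**

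| Reading | Lower end | Upper end |
|---|---|---|
| Two-sided, all variants run (exact, mid-p, asymptotic, continuity-corrected, normal approximations) | .70-.79 | .96-.98 |
| One-sided, exact | .82 | .98 |
| 21-42 taken as the total, two-sided exact | .57 | .90 |
| 21-42 taken as the total, one-sided exact | .70 | .94 |
| Alpha .01, normal approximation | .53 | .90 |
| N = 80, two-sided exact | .60 | .92 |

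None gives both ends. Taking 42 as the total at 60% prevalence would also mean 31.5/60 = 52.5% improvement rather than 70%, and new onset in 10.5/40 = 26% of baseline-negative patients rather than 35%.

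**Step 6. New-onset percentage read as a share of all 100 patients.** The pairs would be 21 against 10 and 42 against 35. The odds ratios are then 2.1 and 1.2, not 3, and two-sided exact power is about .44 and .10.

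**The case against.** The strongest reply is that nothing depends on this figure. The section says that no power analysis was done in advance and that the cohort is all eligible cases. The error is conservative, and the lower end, which is the one that limits the study, reproduces. This stands, and it keeps the practical weight of the point modest.

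The .72 should not be counted as an error. The test variant is unnamed, and .72 lies inside the .70-.79 given by the two-sided variants. This also stands; moving to .71 only aligns the figure with a named exact test.

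The 21-42 can be read as belonging to the no-new-onset sentence that follows it, and the odds ratio of 3 lets a careful reader recover the denominator of the 10-35%. Both are fair in part. However, the count is written without a condition, the denominator has to be inferred, and the more natural reading contradicts the odds ratio. These are points of clarity, secondary to the wrong power figure.

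None of this supports .9. The unnamed variant does not explain it, since every two-sided version gives .96-.98 at that end.

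**Conclusion.** The point holds. From the protocol's own inputs, power at a discordant odds ratio of 3 runs from about .71 to about .97 (two-sided exact, alpha .05, 100 complete pairs), against the stated .72-.9. The upper end is understated by about .07; the lower end agrees to within .01. The discordant pairs in this scenario number 28-56.

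A likely cause is that the improvers-only count of 42 was used as the total at the upper end, while new onset was counted at the lower end. No working is shown, so this is inference, and the conclusion does not depend on it.

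The 10-35% is right as a share of baseline-negative patients and needs to say so. The sample size and the choice of test are unaffected. Under this scenario the weak spot remains signs with about 30% baseline prevalence, where power is about .71; it reaches about .90 at about 45% prevalence.

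**What to change.** In section 7, replace the conservative-scenario sentence with wording such as: *With a discordant odds ratio of 3 (7-14 new-onset cases, i.e. 10-35% of baseline-negative patients; 28-56 discordant pairs in total), two-sided exact McNemar power is about .71-.97.* If the SAP specifies a different McNemar variant, name that one and give its figures instead.

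State that 21-42 discordant pairs applies only when there is no new onset. Beside the conclusion on sufficiency, note that power in the conservative scenario is about .71 at 30% baseline prevalence and about .90 at 45%.

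The cost is a few words. The sample size, tests and endpoints do not change, and the upper power figure becomes more favourable.

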## **8. Statistical Analysis Summary** (Full details in SAP v1.0)

Descriptive statistics will be used to report baseline characteristics by sex. Continuous variables are summarized with mean, standard deviation, median, and range, and categorical variables are summarized with frequencies and percentages.

For the primary endpoints on outpatients only, McNemar tests will be conducted to assess binary variable changes from baseline to 3-month follow-up (e.g. signs/symptoms). Friedman and Wilcoxon signed rank tests will be used to examine the changes of VAS scores over 3 time points. Wilcoxon signed rank tests will also be performed in the other subject-report assessments from baseline to 3-month follow-up. Marginal homogeneity tests will be conducted to compare Nurick and Odom criteria score changes between the two time points.

For the secondary endpoints comparing complication rates between outpatients and inpatients, Fisher's Exact tests will be performed.

## **9. Data Management, Privacy & HIPAA**

- **PHI elements:** After obtaining informed consent to participate in the trial, each participating patient will be de-identified by being assigned a unique number for follow-up.

- **Storage & access:** All data will be stored on hard copy worksheets and spreadsheets available only to the primary author and his nurse practitioner. All study information will be protected according to HIPPA compliance in all instances.
- **De-identification:** participants' unique number is included in the dataset for analysis. No PHI will be shared externally.
- **Retention & destruction:** All data will be preserved for a period of 10 years after completion of the study in compliance with HIPPA rules and the IRB approval. A HIPPA Waiver of Authorization has been approved as it relates to the conduct of the study as delineated in the IRB approval letter.
- **Consent/waiver:** Informed consent will be obtained for all patients involved in the study. Consent for participation in the study is to be obtained prior to surgery. All patients will be informed that de-identified outcome data will be compiled in all surgical cases to compare with previously published statistics for purposes of patient education and pre-operative teaching. They are not obligated to participate in the data collection process and may opt out at any point in their treatment.

## **10. Monitoring & Quality Assurance**

This project is at minimal risk level, and no DSMB is required. For quality control, adverse events are recorded per our clinic policy. Periodic data checks will be performed monthly to insure data is being collected as to protocol and according to HIPPA compliance,

## **11. Registration & Dissemination**

This study was reviewed by the MetroWest Medical Center Institutional Review Board and approved with a reference number of 2025-919. As this is an observational study, it does not require a clinical trial registration. Results will be submitted to NEJM. SAP v1.0 and Protocol 1.0 are provided as Supplementary Appendix.

